3. STUDY DESIGN

This is a phase III, randomized, double-blind, placebo-controlled, multicenter, 7-month study designed to assess the safety and efficacy of intramuscular injections of VM202 in the calf of diabetic patients with chronic nonhealing foot ulcers and concomitant PAD. Subjects with confirmed PAD and diabetes aged \geq 18 years to \leq 80 years diagnosed with nonhealing foot ulcers will be screened for study eligibility after giving informed consent.

At Screening, standard of care will be initiated that will continue for the duration of the study, as follows:

- Surgical debridement of necrotic tissue or devitalized tissue
- Use of appropriate off-loading when ambulating
- Maintenance of moist wound environment

Three hundred patients (from up to 30 study centers) who meet the eligibility criteria will be randomized in a 2:1 ratio to one of two treatment groups: 200 patients with VM202 (16 mg) plus standard of care or 100 subjects with placebo plus standard of care, respectively. Safety will be monitored throughout the study by an independent Data Safety Monitoring Board (DSMB, Section 8.5).

Patients will receive intramuscular injections in the ipsilateral calf of the affected foot with the target ulcer of either VM202 or placebo on Day 0, Day 14, Day 28, and Day 42 as follows:

Treatment: Days 0, 14, 28, and 42

TREATMENT]	DOSE VM20	FINAL DOSE		
GROUP	DAY 0	DAY 14	DAY 28	DAY 42	VM202 (mg)
VM202	4	4	4	4	16
Placebo	0	0	0	0	0

0 indicates injections of Placebo

VM202 will be delivered in a solution of 0.5 mg VM202 / mL. All subjects will receive sixteen (16) 0.5-mL intramuscular injections of VM202 or placebo at each injection visit.

The schedule of study visits and the clinical parameters that will be measured at the visits are summarized in Table 1 to Table 3 below.

The subjects' target ulcer will be evaluated by photograph, surface area, depth, perimeter and volume measurements. Subjects must have a non-healing ulcer on Day 0 that meets study entry inclusion criterion # 5 and does not meet exclusion criterion #6 to be eligible for study participation. Subjects will continue to come to the clinic once a week for dressing changes and wound assessment until the ulcer has healed or study exit, whichever comes first. Measurement of the target ulcer will be performed at each follow-up visit until complete wound closure or study exit.

Further details on the study procedures and conduct are provided in the protocol.

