8.6.3. Missing Dates and Times

If a start or stop date for an adverse event or a concomitant medication is completely missing, it will not be imputed. If that date is partially missing, imputed dates specified in Table 6 will be used to derive the duration of the adverse event or the duration of the medication use. If the start or stop date for an adverse event is not missing but the corresponding time is partially or completely missing, imputed times specified in Table 7 will be used to derive the duration of the adverse event. For adverse event attribution relative to a specific injection, a missing start date and time should default to the date and time of the immediately documented prior injection. Missing years will not be estimated under any conditions.

Table 6 Imputation Rules for Partial Adverse Event or Concomitant Medication Start and Stop Dates

	Missing	IMPUTATION	EXCEPTION
Start Date	Day	01	Default to Study Day 0 (day of first injection procedure) if an event starts in the same year and month as Study Day 0
	Day/Month	01JAN	Default to Study Day 0 if an event starts in the same year as Day 0
Stop Date	Day/Month	Last day of the month	Default to the End of Study Date if the imputed event stop date is after the End of Study Date or before start day of the event
	Day/Month	31DEC	Study Date or before start day of the event

Table 7 Imputation Rules for Partial or Missing Adverse Event Start and Stop Times

	Missing	IMPUTATION	EXCEPTION
Start Time	Minute	00	Default to time of first injection if an event
	Hour: Minute	00:00	starts on Study Day 0
Stop Time	Minute	59	(none)
	Hour: Minute	23:59	Default to 23:59 on the End of Study Date if
			the imputed event stop date is after the End
			of Study Date or before start day of the event

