9.5. Safety Analyses

No formal statistical testing will be conducted for the safety analyses. The following sections summarize the descriptive analysis presented for these safety endpoints. All subjects in the safety population will be included in these analyses, with subjects grouped by the actual treatment received. All summaries will be derived based on available data at scheduled visits; safety data at unscheduled visits will only be included in data listings. No imputation will be performed for missing values.

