9.5.3. Adverse Events

Adverse events will be collected once subjects meet all the study eligibility criteria and are randomized and administered study drug. However, all adverse event summaries will be restricted to Treatment-Emergent Adverse Events (TEAE), which are defined as those AEs that occurred after first dosing and those pre-existing conditions that worsened during the study. If the start time for an AE that occurs on the first date of dosing is unknown, then the event will be assumed to be a TEAE. If the start date of an AE is unknown, the event will be assumed to be a TEAE.

The number of subjects experiencing a particular event, the percentage of subjects experiencing the event, and the total number of events will be presented. The following summaries will be created:

- Overall summary of TEAEs, which includes the subject incidence of TEAEs and total number of unique TEAEs from each of the following AE summaries without regard to MedDRA system organ class or preferred term
- TEAE by SOC and preferred term
- TEAE by SOC and preferred term by injection number. Subjects and events are attributed to a given injection only if the event start date (subject to the missing date and

time imputation rules of Section 8.6.3) occurs on or after the date and time of that injection and not before the next injection.

- TEAE by SOC, preferred term and protocol version
- TEAE by SOC, preferred term and maximum severity. At the across-SOC and preferred term levels of subject summarization, a subject is classified according to the highest severity if the subject reported one or more events; severity within an SOC is not summarized. AEs with missing severity will be considered severe for this summary.
- TEAE by SOC, preferred term and closest relationship to study treatment (Related/Not Related). At each level of subject summarization, a subject is classified according to the closest relationship if the subject reported one or more events. AEs with a missing relationship will be considered 'related' for this summary; events classified as 'possibly', 'probably' or 'definitely' will be considered 'related'.

A listing of treatment-emergent SAEs (if any) will be provided, and if more than one occurs within any given preferred term, a summary of treatment-emergent SAEs by SOC and preferred term will be created.

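### SAP 8.6.3 does not settle which dose an adverse event belongs to when it starts on Day 14, 28 or 42 with no clock time; read literally, it goes to the previous injection

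*SAP*

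**What the plan says.** Three pieces of the SAP bear on this.

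- **Table 7 (8.6.3).** For an adverse event with a known start date, a missing minute becomes 00 and a wholly missing time becomes 00:00. The only start-time exception is "Default to time of first injection if an event" starts on Study Day 0. The text gives the purpose of the table: "imputed times specified in Table 7 will be used to derive the duration of the adverse event".
- **Attribution sentence (8.6.3, same paragraph).** For tying an event to a particular injection, "a missing start date and time should default to the date and time of the immediately documented prior injection". It does not mention the case where the date is known and only the time is missing.
- **By-injection summary (9.5.3).** An event counts towards an injection only if its start, after imputation under 8.6.3, "occurs on or after the date and time of that injection and not before the next injection". The reference is to the 8.6.3 rules as a whole; 9.5.3 does not say which of them governs.

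Injections of "either VM202 or placebo on Day 0, Day 14, Day 28, and Day 42 as follows" (SAP 3), so three of the four injection days lie outside the Table 7 exception.

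**The concern.** Midnight precedes any injection given during clinic hours. If the Table 7 value feeds the by-injection table, an untimed event on Day 14, 28 or 42 falls into the window of the dose given about 14 days earlier, even if it began an hour after that day's injection. The SAP handles the same-day problem for the first dose and provides nothing equivalent for the other three.

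Same-day events are expected data. Under Protocol 3.4.8 and 3.4.10 to 3.4.12, adverse events are assessed 1 to 3 hours after each injection. Protocol 5.2 lists the date of onset among the items to record but no time of onset, so missing times are plausible. That is an inference, since the adverse event form is not in the documents.

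At stake is whether the by-injection table shows reliably if events cluster after particular doses. There is also a reproducibility problem: two programmers could both follow the SAP and produce different tables.

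**Working it through.** The plan gives no figure to reproduce, so the check applies the rules to a timeline.

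**Inputs.** Injection days 0, 14, 28 and 42 (SAP 3); Table 7 and the attribution sentence (8.6.3); the window in 9.5.3. Assumption: injection at 10:20 each time. For a wholly missing time, any injection time after 00:00 gives the same result.

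**Reading of the window.** Taken word for word, the closing condition in 9.5.3 requires an event to fall on or after the next injection. An event two hours after the Day 14 injection would then be credited to Day 0. The evident intent is before the next injection, so each event is assigned to the latest injection at or before its imputed start.

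**Date known, hour and minute missing.** Three readings of 8.6.3:

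- A: Table 7 supplies the time; the attribution sentence applies only if date and time are both missing.
- B: the attribution sentence also covers a missing time alone, and a same-day injection counts as prior.
- C: as B, but a prior injection must be on an earlier date.

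| Event dated | A | B | C |
|---|---|---|---|
| Day 0 | Day 0 | Day 0 | Day 0 |
| Day 14 | Day 0 | Day 14 | Day 0 |
| Day 28 | Day 14 | Day 28 | Day 14 |
| Day 42 | Day 28 | Day 42 | Day 28 |

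A is the closest to the words. The paragraph distinguishes a missing date from a known date with a missing time, and Table 7 is the only rule written for the second case.

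**Only the minute missing (reading A).** Recorded hour 10 on Day 14 becomes 10:00, before 10:20, so the event goes to Day 0. Recorded hour 8 becomes 08:00 and also goes to Day 0, correctly. Recorded hour 11 becomes 11:00 and goes to Day 14, correctly. Only the hour of the injection is a problem.

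**Effect on the table.** Let a, b and c be the numbers of untimed events on Days 14, 28 and 42 that in truth followed that day's injection. Under A or C the event counts change by:

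- injection 1: +a
- injection 2: −a + b
- injection 3: −b + c
- injection 4: −c

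The sum is zero: events are relocated, not lost. The documents give no basis for values of a, b or c. SAP 1 reports 7 + 5 + 16 + 16 = 44 subjects enrolled, so the counts are likely to be small.

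**The case against.** The strongest reply is that Table 7 was not written for this purpose. Its stated use is duration, and the sentence that follows is expressly about attribution. If that sentence covers a missing time alone and a same-day injection counts as prior, nothing moves. It is also hard to apply when the date is wholly missing, because nothing then anchors which injection came before; that suggests a wider intended scope. This stands in part. It makes the shift one reading rather than a certainty, but it does not remove the ambiguity, because the sentence names date and time together and 9.5.3 does not choose between the rules.

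A reader might also infer that tolerability by dose would be obscured, with injection 1 inflated and injection 4 emptied. The documents do not support that.

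- Local and hypersensitivity reactions are graded under Protocol 4.2.11. SAP 9.5.2 summarises them by visit and by pre- and post-injection assessment, with no imputed clock times.
- The by-injection rows are already unequal: injections 1 to 3 each cover about 14 days, while injection 4 runs from Day 42 to Day 210, which is 210 − 42 = 168 days. Losing same-day events would not empty it.

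Nor is the previous dose always wrong. Protocol 3.4.10.1, 3.4.11.1 and 3.4.12.1 require an adverse event assessment before the injection on Days 14, 28 and 42. Day 0 differs because events before the first injection are medical history (Protocol 5.2 and 5.3). Copying the Day 0 exception unchanged to the later doses would credit some events to a dose not yet given.

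**Conclusion.** The point holds as an unresolved rule whose most literal reading credits untimed events on Days 14, 28 and 42 to the previous injection. It does not hold as a certain misassignment.

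The size is one dose per affected event, in one descriptive summary; SAP 9.5 states "No formal statistical testing will be conducted for the safety analyses". An event on Day 14 or later is treatment-emergent under any reading, so treatment-emergent status and overall event rates are unchanged. So are the injection-site tables and all efficacy analyses. The frequency cannot be estimated from the documents.

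The conclusion assumes that 9.5.3 means before the next injection and that some start times will be missing. Severity minor; confidence moderate.

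**What to change.** Add a rule to 8.6.3 that applies only to by-injection attribution and leaves Table 7 in place for duration:

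- If an event starts on any injection day and both hour and minute are missing, assign it that day's injection time. If it was recorded at the pre-injection assessment, credit it to the previous injection instead.
- If only the minute is missing, keep the recorded hour. Use the injection time only when the recorded hour is the hour of the injection.

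In 9.5.3, refer to this rule by name and, in the same edit, reword the end of the window to say before the next injection.

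The cost is a few lines of SAP text and a small programming condition. The database must show at which assessment an event was recorded, which the documents do not confirm. The downside is small: a few events that truly began before a same-day injection may be credited to it.

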9. STATISTICAL METHODS

9.1. General Principles of Data Analyses

The primary analyses of the efficacy endpoints (Sections 9.4.1.1, 9.4.4) will be based on the ITT population. Additional sensitivity analyses for the primary efficacy endpoint, utilizing other populations and/or different ways of handling missing data, will be performed to further assess the effects of the treatment (Section 9.4.1.2). Supportive subgroup and covariate-adjusted analyses of the primary efficacy endpoint in the ITT population are described in Sections 9.4.2 and 9.4.3, respectively. Analyses of the safety outcomes (Section 9.5) will be based on the safety population.

The statistical analyses will be reported using summary tables, figures and listings. Continuous variables will be summarized with means, standard deviations, medians, minimums, maximums, and number of non-missing observations for each treatment group. Other selected percentiles, such as the 25th percentile and 75th percentile, may be presented for parameters that are not normally distributed or are suspected of exhibiting that tendency. Categorical variables will be summarized by counts and the percentage of subjects in corresponding categories. All data collected, including for subjects screened but not randomized, will be included in data listings.

All inferential statistical analyses will be performed with a two-sided confidence level of 95% or a two-sided significance level of 0.05.

All analyses and tabulations will be performed using SAS® Version 9.3 or higher on a PC platform.

9.2. Subject Enrollment and Disposition

Subject disposition will be summarized for all the randomized subjects, including the number and percentage (based on the total number of subjects randomized) of subjects in each of the following categories:

- Early Termination based on the ITT population
- Safety, ITT, mITT, and PP populations

Major protocol deviations for subjects not in the PP populations will be listed.

9.3. Demographics and Baseline Characteristics

The following outcomes will be summarized by the standard methods for continuous and categorical variables described in Section 9.1.

The demographics include the following parameters:

- Age at informed consent
- Sex
- Race
- Ethnicity

The baseline characteristics include the following:

- Wound location
- Baseline wound volume
- Baseline ABI
- Baseline TBI
- Toe pressure categorized by assessment method (Doppler, PPG)

- TcPO₂ (collected at a subset of study centers)
- Baseline BMI
- Baseline HbA1c
- Vital signs: blood pressure, weight, BMI, heart rate, respiration rate, temperature
- Medical history categorized by MedDRA system organ class (SOC)
- 12-lead EKG Interpretation: Normal, Abnormal NCS, Abnormal CS
- Urine pregnancy test: Positive, Negative, and Not Applicable

These parameters will be summarized by treatment group for the ITT population and included in data listings. Other collected baseline characteristics will be listed only.

9.4. Efficacy Endpoint Analyses

9.4.1. Primary Efficacy Endpoint

The primary efficacy endpoint is the proportion of subjects with a target wound closure by the 4-month follow-up (responder). The responder rate will be compared between the two treatment groups (VM202 and placebo).

9.4.1.1. Primary Analysis of the Primary Efficacy Endpoint

The primary analysis for the responder rate will be based on the ITT population.

Fisher's exact test will be used to compare the responder rate between the treatment groups. The 95% confidence interval of the responder rate of each treatment group will be derived using the binomial distribution and the 95% confidence interval of the responder rate difference will be calculated.

Subjects whose status of wound closure cannot be assessed at 4 months (e.g., due to earlier discontinuation from the study), will be considered non-responders.

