3.4.7. RANDOMIZATION AND BLINDING

A randomization schedule with subjects allocated to VM202 (treatment) or placebo (control) in a 2:1 ratio will be used.

The Pharmacist will review the subject's treatment allocation and assigned kit number in IWRS. All documents related to investigational product and treatment allocation will be kept in a secure location with access limited to Pharmacy personnel responsible for preparing the syringes with assigned study treatment.

After study initiation, VM202 and VM202 vehicle (placebo) will be provided to the site's pharmacy. Depending on the assigned study treatment, syringes of VM202 or placebo will be prepared after the clinic notifies the Pharmacy that the subject has arrived in the clinic to undergo study treatment.

This is a double-blind study. The patients, Investigators, study site staff, or Sponsor or any of the Sponsor's representatives or vendors will not know the assigned treatment. Blinding will be achieved by having the study medication (VM202) prepared by the study pharmacist or designee. Reconstituted VM202 is indistinguishable from VM202 vehicle (placebo). The site pharmacist or designee prepares the vials according to the instructions. The site pharmacist or designee and select individuals at the CRO (but excluding blinded study monitors and the blinded clinical trial manager) will be unblinded to the treatment assignments. The subject and study personnel, including core labs, principal investigator, co-investigators, study coordinators, study monitors, data managers, and the clinical trial manager will remain blinded until all data have been entered into the database and the database is locked.

IN CASE OF EMERGENCY ONLY, i.e., SERIOUS ADVERSE EVENT (SAE) AND ONLY WHEN THIS INFORMATION INFLUENCES THE SUBJECT'S

MANAGEMENT AND WHEN KNOWLEDGE OF THE TREATMENT ASSIGNMENT IS ESSENTIAL TO THE WELFARE OF THE PATIENT, the Investigator or designee may request unblinding of that patient. Whenever feasible, the Sponsor (or the Sponsor's representative) should be consulted in advance of breaking the blind for any patient. In any case, the Sponsor (or the Sponsor's representative) must be notified of the unblinding, and the Investigator or designee will document the reason(s) necessary to break the blind for any patient. Complete instructions on this process are detailed in the Study Reference Manual (VMNHU-003 Subject Emergency Unblinding Communication Plan).

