4. STUDY ENDPOINTS

4.1. Primary Efficacy Endpoint

The primary efficacy endpoint is the proportion of subjects with a target wound closure by the 4-month follow-up.

The statistical hypotheses for the primary efficacy endpoint are:

 H_0 : $P_t = P_c$ versus H_a : $P_t \neq P_c$

where P_t and P_c are the proportions of subjects with a target wound closure by the 4-month follow-up for the VM202 and placebo groups, respectively.

The hypothesis testing will be at a two-sided alpha of 0.05.

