4.5. Planned Covariates

The primary efficacy endpoint will be analyzed by adjusting for each of the following covariates separately and all covariates simultaneously using the methods described in Section 9.4.3:

- Wound location (medial malleolus, lateral malleolus, ankle flexure, posterior ankle, dorsum of foot, sole of foot, medial aspect of foot, lateral aspect of foot, big toe, 2nd through 5th toes [collapsed]; these locations have been re-examined and were recategorized based on the distribution and clinical considerations prior to database lock. Data will be summarized as weight bearing (plantar foot surface), and not weight-bearing (non-plantar foot surface).
- Age (\leq median and > median)
- Baseline wound area (≤ median and > median)

5. **DEFINITIONS**

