6. SAMPLE SIZE CALCULATION

Based on prior VM202 studies, the percentage of subjects achieving complete wound closure by the 4-month follow-up (i.e., 4-month responder rate) for VM202 (treatment arm) is assumed to range from 50% to 60%, and that for the placebo group is assumed to range from 20% to 30%. Table 4 below summarizes the statistical power for a sample size of 200 VM202 and 100 placebo subjects based on Fisher's exact test with a two-sided significance level of 0.05 for the statistical hypothesis specified in Section 4.1.

Table 4 Statistical power by estimated responder rates for Treatment (pt) and Control (pc) arms

Pt	рc	Statistical Power
0.50	0.20	>.999
0.50	0.25	0.985
0.50	0.30	0.898
0.55	0.20	>.999
0.55	0.25	0.999
0.55	0.30	0.982
0.60	0.20	>.999
0.60	0.25	>.999
0.60	0.30	0.998

Except for the assumption of $p_t = 0.50$ and $p_c = 0.30$, the statistical power for all assumptions of p_t and p_c is > 0.95. For the assumption of $p_t = 0.50$ and $p_c = 0.30$, the statistical power is about 90%.

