8.4. Multiplicity Adjustment

No multiplicity adjustment will be performed since the study has one primary efficacy endpoint with one primary population and analysis method. Sensitivity analyses for the primary efficacy endpoint are supportive and analyses for other efficacy endpoints are exploratory.

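### The primary test of wound closure is valid but unadjusted, although baseline ulcer area is measured before randomisation and is already a planned covariate; the cost is some power and an estimate that keeps any chance imbalance in ulcer size

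*SAP*

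**What the plan says.** SAP 4.1 defines one endpoint, closure by the 4-month follow-up, and states: "The hypothesis testing will be at a two-sided alpha of 0.05". SAP 9.4.1.1 gives the confirmatory analysis in the ITT population: "Fisher's exact test will be used to compare the responder rate between the treatment groups". SAP 8.4 relies on this being the only one, since "the study has one primary efficacy endpoint with one primary population and analysis method". The first sensitivity model (SAP 9.4.1.2.1) is a logistic regression on treatment alone, so it is unadjusted too.

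Baseline wound area does appear in the plan. SAP 4.5 lists it, split at the median, with wound location and age, and says: "The primary efficacy endpoint will be analyzed by adjusting for each of the following covariates separately and all covariates simultaneously". SAP 9.4.2 plans a Cochran–Mantel–Haenszel (CMH) test for each subgrouping variable, area included, and SAP 7.5 calls the subgroup analyses exploratory. SAP 9.4.3 specifies a logistic model with all the covariates together. SAP 9.1 sets the rank of both: "Supportive subgroup and covariate-adjusted analyses of the primary efficacy endpoint in the ITT population".

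Protocol 3.4.8.1 has the ulcer's surface area documented on Day 0 before the subject is randomised. Protocol 3.4.7 says only that a schedule "in a 2:1 ratio will be used". It names no stratification factor and, like Protocol 3.2, leaves operational detail to the IWRS manual.

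**The concern.** The size of the ulcer at baseline is the starting state of the thing the endpoint measures. Entry allows 0.5 to 15 cm² at Screening, a 30-fold range. The SAP adjusts its exploratory measures of wound volume, perimeter, area and depth for their own baseline values (SAP 9.4.4.3 and 9.4.4.4), but not the primary endpoint, and gives no reason. The baseline table in SAP 9.3 lists wound volume and not area, so an imbalance in area would not be summarised there.

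If area predicts closure, an unadjusted comparison leaves explainable variation in the noise, and the primary risk difference carries whatever size imbalance randomisation happened to produce. This matters more because SAP 1 reports 7 + 5 + 16 + 16 = 44 subjects enrolled and SAP 10 says the study stopped early. A supportive adjusted result cannot take the place of the primary one.

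**Working it through.** **Inputs from the documents.** Two-sided alpha 0.05 (SAP 4.1); a "sample size of 200 VM202 and 100 placebo subjects" with closure of 50% to 60% on VM202 and 20% to 30% on placebo (SAP 6); 44 enrolled (SAP 1).

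**Assumptions.** A 29:15 split of the 44 (44 × 2/3 ≈ 29). A correlation ρ between log baseline area and closure of 0.3 to 0.5, because the documents give none. At 43% closure, ρ = 0.5 is an odds ratio of about 3.9 per SD of log area, which is strong.

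**1. The plan's own figure.** The arcsine approximation for Fisher's test at 50% v 30% is

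z = √(4·200·100/300) × [asin√(0.50 − 1/400) − asin√(0.30 + 1/200)] − 1.96 = 16.33 × (0.7829 − 0.5851) − 1.96 = 1.27, so power = Φ(1.27) = 0.898.

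This is the value in SAP Table 4, and the other eight rows also agree. Full enumeration of Fisher's test gives 0.918, which is the right comparator for an adjusted test.

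**2. Type I error.** By enumeration with both rates at 30%, Fisher's test has size 0.043 at 200:100 and 0.035 at 29:15. A test that permutes treatment labels on the residuals from a regression of closure on log area has simulated size 0.051 to 0.052 at 29:15.

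**3. Power at 200:100, 50% v 30%.** The adjusted permutation test reaches about 0.93 to 0.94 at ρ = 0.3, 0.95 to 0.96 at ρ = 0.4 and 0.97 at ρ = 0.5. Against 0.918 the gain is about 2 to 5 points (0.94 − 0.918 = 0.022; 0.97 − 0.918 = 0.052). A second simulation used odds ratios of 1.5, 2 and 3 per SD (ρ about 0.19 to 0.44) and a logistic score test. It gave 0.928, 0.944 and 0.961 against Fisher's 0.918, 0.922 and 0.916, a gain of 1.0 to 4.5 points. With area not prognostic it gave 0.918 v 0.916. All other rows of Table 4 are already at 0.98 or more.

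**4. Power at 29:15.** The fourth column is the same permutation test with an uninformative covariate. It separates the effect of adjustment from that of Fisher's discreteness.

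| Closure rates | Fisher (exact) | Adjusted, ρ 0.3 to 0.5 | Uninformative covariate | Total gain over Fisher | From adjustment |
|---|---|---|---|---|---|
| 50% v 30% | 0.165 | 0.26 to 0.28 | 0.22 | 9 to 12 points | 4 to 6 points |
| 55% v 25% | 0.369 | 0.52 to 0.59 | 0.47 | 15 to 22 points | 5 to 12 points |
| 60% v 20% | 0.638 | 0.78 to 0.85 | 0.74 | 14 to 21 points | 4 to 11 points |

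Simulation error is a point or more per cell. Repeat runs at 50% v 30% put the part due to adjustment between about 2 and 9 points; about 3 to 7 is a fair summary. The score-test simulation agrees on the split. At 50% v 30%, an unadjusted chi-square test already gives 0.253 to 0.262, and adding area raises it to 0.256 to 0.297, a further 0.3 to 3.5 points.

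**5. Chance imbalance.** The SD of the standardised difference in log area is √(1/29 + 1/15) = 0.318 at 29:15 and √(1/200 + 1/100) = 0.122 at 200:100. An imbalance above 0.25 SD has probability 43% and 4% respectively. With a pooled rate of (2 × 50% + 30%)/3 = 43%, a one-SD imbalance at 29:15 shifts the raw risk difference by 0.318 × ρ × √(0.43 × 0.57):

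- ρ = 0.3: 4.7 points
- ρ = 0.5: 7.9 points; a 1.96-SD imbalance gives 1.96 × 7.9 ≈ 15 points

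**The case against.** The strongest reply is that nothing here is an error. Fisher's test in the ITT population is pre-specified and valid, and it is the test the sample size was built on. Chance imbalance is already part of its error rate and adds noise, not bias. That stands: the point concerns efficiency and the quality of the estimate.

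It also stands that adjustment for area is planned, through the CMH test in SAP 9.4.2 and the logistic model in SAP 9.4.3. A reader might infer that the plan ignores ulcer size. It does not; no adjusted analysis is primary.

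Three stronger readings are tempting, and the documents do not support them:

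- **That chance imbalance at 44 subjects could match a treatment effect worth detecting.** Even a 1.96-SD imbalance at ρ = 0.5 shifts the difference by about 15 points. The smallest difference in SAP Table 4 is 50% − 30% = 20 points, and the documents define no smaller relevant effect.
- **That the whole gain at 44 subjects comes from adjustment.** Much of it comes from replacing a conservative discrete test.
- **That randomisation was unstratified.** The protocol names no factor, but the IWRS manual is not among the documents.

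Finally, power at 44 subjects stays low at 50% v 30% whichever test is used, and a late change of primary method costs credibility. Both are fair and limit the benefit, but neither removes it.

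**Conclusion.** The point holds as one of efficiency. The only confirmatory test leaves out a prognostic candidate that the plan already measures and names. At the planned size the loss is small: about 2 to 5 points in the least favourable row of Table 4 and almost nothing elsewhere. At 44 subjects the proposed change gains about 9 to 22 points over Fisher's test. Adjustment itself supplies about 3 to 7 of these at 50% v 30% and about 4 to 12 at 55% v 25% and 60% v 20%. A one-SD chance imbalance moves the unadjusted risk difference by about 5 to 8 points, which is less than any difference in Table 4.

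These figures rest on the assumed ρ of 0.3 to 0.5 and the assumed 29:15 split. If area does not predict closure, the gain from adjustment is near zero. Validity is not in question.

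**What to change.** Before unblinding, and documented as a blinded change, amend SAP 9.4.1.1 as follows:

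1. Adjust the primary test for log baseline wound area as a continuous variable: regress closure on log area without treatment, then compare mean residuals between arms. A median split discards part of the gain (CMH 0.948 v continuous 0.961 at 200:100 with an odds ratio of 3 per SD).
2. Take the p-value from re-randomisation that follows the actual randomisation scheme, including any stratification in the IWRS specification.
3. State which Day 0 area is used. Protocol 3.2 has the ulcer documented before and after debridement, while Protocol 3.4.8.1 does not say which.
4. Report the area-adjusted (standardised) risk difference with its 95% CI as the primary estimate, and keep the unadjusted Fisher test as a sensitivity analysis.
5. In the same edit, reconcile SAP 4.5, which promises adjustment for each covariate separately as well as jointly, with SAP 9.4.3, which specifies only the joint model, and add baseline area to the SAP 9.3 summary.

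The cost is SAP wording and a short program, with no new data or patients. The downsides are a late change to the primary method, a non-standard p-value that may occasionally disagree with the confidence interval at small N, and little gain if area predicts closure only weakly. If the blind is already broken, the primary test should stay as it is and the adjusted analysis be reported as supportive.
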